### **Electrolyte metabolism adverse events**

High levels of cortisol also exert mineralcorticoid (aldosterone) activity, stimulating absorption of sodium and excretion of potassium at the renal collecting tubules. Hypokalemia is most often associated with Cushing's syndrome due to ectopic ACTH production. Patients with pituitary corticotroph tumors may present with mild hypokalemia (3.0-3.5 mmol/L). Hypokalemia associated with seliciclib appeared to be dose dependent, occurring only in doses higher than 1200 mg b.i.d. 3 days per every 2 weeks. Patients who develop serum potassium values consistently  $<3.0$  mmol/L in spite of appropriate therapeutic interventions are discontinued from the study.

### **Dermatologic (skin) adverse events**

Significant skin adverse events (Grade 3 or more) resulting from seliciclib are rare (<1%). For NCI-CTCAE v3.0 Grade 4 rash manifested as toxic epidermal necrolysis (i.e. Stevens-Johnson's Syndrome etc) seliciclib must be permanently discontinued. Subjects with poorly tolerated skin adverse events may be successfully managed by providing a brief (up to 14 days) therapy interruption; the daily dose of seliciclib should then be reinstated. However, the rash may improve without the need for interrupting therapy with seliciclib. A variety of agents can be used to manage skin rashes. These include mild-to-moderate strength steroid creams, topical or systemic antibiotics, topical or systemic antihistamines, and occasionally, retinoid creams. There is no standard, known, or established treatment proven effective for drug-related skin rashes or changes due to seliciclib. The need for oral or topical antibiotics will be a clinical decision of the investigator and should be preceded by a culture of affected areas and, if

indicated, a dermatology consultation. Oral steroids will be strongly discouraged. Other options for treatment of significant rashes may be determined upon consultation with dermatologist.

### **Gastrointestinal adverse events**

If GI adverse events are not appropriately managed, they may be associated with the development of dehydration. Management of gastrointestinal adverse events is discussed in detail in below.

#### **Nausea, vomiting, or both**

In subjects who have emesis and are unable to retain seliciclib, every attempt should be made to obtain control of nausea and vomiting. A dose may be repeated if tablets can be visually found after the vomiting episode.

## **PHARMACEUTICAL INFORMATION**

### **Seliciclib (NSC # )**

**Chemical Name:** 2-(R)-(1-Ethyl-2-hydroxyethylamino)-6-benzylamino-9-isopropylpurine

**Other Names:** CYC202

**Mode of Action:** Selective CDK inhibitor

**How Supplied:** 200 mg/capsule

**Storage:** Cross reference [IND No. 71,011-CYC202(R-roscovitine or Seliciclib)].

**Stability:** Cross reference [IND No. 71,011-CYC202(R-roscovitine or Seliciclib)].

**Route of Administration:** Oral

## **REGULATORY AND REPORTING REQUIREMENTS**

It is the responsibility of the investigator to document all adverse events, which occur during the investigation. An adverse event is any untoward medical occurrence in a patient or clinical investigation subject, temporally associated with the use of the medicinal product, whether or not considered related to the medicinal product. *An AE can therefore be any unfavorable and unintended sign (including an abnormal laboratory finding), symptom, or disease (new or exacerbated) temporally associated with the use of a medicinal product.* Anticipated day-to-day fluctuations of the disease under study that do not represent a clinically significant exacerbation or worsening need not be considered an adverse event.

All adverse events occurring from the first dose of investigational product until five days after the last dose will be recorded **REGARDLESS OF WHETHER OR NOT THEY ARE CONSIDERED DRUG RELATED.** In addition, any SAEs, which occur as a result of protocol specific diagnostic procedures or interventions will also be reported.

### **Assessment of Causality**

Every effort will be made by the investigator to explain each adverse event and assess its relationship, if any, to study drug treatment. Causality will be assessed using the following categories: no (not related), or yes (reasonable possibility).

The degree of certainty with which an adverse experience is attributed to drug treatment (or alternative causes, e.g. natural history of the underlying diseases, concomitant therapy, etc.) will be determined by how well the experience can be understood in terms of the following:

- Known pharmacology of the drug
- Reaction of similar nature being previously observed with this drug or class of drug
- The event having often been reported in literature for similar drugs as drug related (e.g. skin rashes, blood dyscrasias)
- The event being related by time to drug administration terminating with drug withdrawal (dechallenge) or reproduced on rechallenge.

The investigator may change his/her opinion of causality in light of follow-up information, amending the SAE form. The causality assessment is one of the criteria used when determining regulatory reporting requirements.

### **Following-up of Adverse Events**

Investigators should follow-up subjects with adverse events until the event has subsided (disappeared) or until the condition has stabilized.

### **Definition of Serious Adverse Events:**

A serious adverse experience is any event, which is fatal, life threatening, disabling or incapacitating or results in hospitalization, prolongs a hospital stay or is associated with congenital abnormality. In addition, any experience which the investigator regards as serious or which would suggest any significant hazard, contraindication, side effect or precaution that may be associated with the use of the drug should be reported as a serious adverse event. Examples of such events are invasive or malignant cancers, intensive treatment in an emergency room or at home for allergic bronchospasm, blood dyscrasias or convulsions that do not result in hospitalization, or development of drug dependency or drug abuse.

Abnormal laboratory findings (e.g., clinical chemistry, hematology) or other abnormal assessments (e.g., x-rays, scans, vital signs, etc.) that are judged by the investigator as **clinically significant** will be recorded as AEs or SAEs if they meet the definition of an AE or SAE.

### **Life threatening definition:**

An adverse event is life threatening if the patient was at immediate risk of death from the event as it occurred (i.e. it does not include a reaction that if it had occurred in a more serious form might have caused death). For example, drug-induced hepatitis that resolved without evidence of hepatic failure would not be considered life threatening even though drug-induced hepatitis could be fatal.

### **Disability/incapacitating definition:**

An adverse experience is incapacitating or disabling if the experience results in a substantial and/or permanent disruption of the patient's ability to carry out normal life functions.

### **Hospitalization definition:**

Hospitalization for elective treatment of a pre-existing condition that did not worsen from baseline is not considered an AE.

### **Additional SAE definitions**

- All Grade 4 laboratory abnormalities  
- Hepatobiliary events have been seen in subjects taking seliciclib. As a precaution, the following will be reported as an SAE:

- ALT  $>3 \times$  ULN and total bilirubin  $>2.0 \times$  ULN ( $>35\%$  direct; bilirubin fractionation required).
- Other hepatic events should be documented as an AE or an SAE as appropriate. SAEs, pregnancies, and liver function abnormalities meeting pre-defined stopping criteria will be reported promptly to Cedars-Sinai Office of Research Compliance as described in the following table once the investigator determines that the event meets the protocol definition for that event.

### **Reporting Serious Adverse Events**

Any serious adverse events, which occur during the clinical study or within 5 days of receiving the last dose of study medication, whether or not related to the study drug, will be reported by the investigator. In addition, any SAEs, which occur as a result of protocol specific diagnostic procedures or interventions will also be reported.

### **Lack of Efficacy**

“Lack of efficacy” *per se* will not be reported as an AE. The signs and symptoms or clinical sequelae resulting from lack of efficacy will be reported if they fulfill the AE or SAE definition.

### **All serious adverse events will be reported to the FDA, Cedars-Sinai Office of Research Compliance and Cyclacel Pharmaceutical, Inc. by the investigator.**

The SAE report will comprise a full written summary, detailing relevant aspects of the adverse events in question. Where applicable, information from relevant hospital case records and autopsy reports will be included. Follow-up information will also be forwarded within 24 hours.

SAEs brought to the attention of the investigator at any time after cessation of seliciclib and considered by the investigator to be related or possibly related to seliciclib will be reported if and when they occur. Additionally, SAEs that are related to study participation (e.g., procedures, invasive tests, change from existing therapy) or are related to a concurrent medication will be collected and recorded from the time the subject consents to participate in the study until he/she is discharged.

### **Pregnancy**

Patients who become pregnant during the study should discontinue the study immediately. Patients should be instructed to notify the investigator if it is determined after completion of the study that they become pregnant either during the treatment phase of the study or within five days after the treatment period. Whenever possible a pregnancy should be followed to term, any premature termination reported, and the status of the mother and child after delivery reported.

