- Patients who have clinically significant impairment in cardiovascular function or are at risk thereof, as evidenced by
  - Congestive heart failure (NYHA Class III or IV), unstable angina, sustained ventricular tachycardia, clinically significant bradycardia, high grade AV block, history of acute MI less than one year prior to study entry
- Patients with liver disease or history of liver disease such as cirrhosis, chronic active hepatitis B and C, or chronic persistent hepatitis, or patients with ALT or AST more than  $1.5 \times ULN$ , serum total bilirubin more than  $ULN$ , serum albumin less than  $0.67 \times LLN$  at screening
- Serum creatinine  $\geq 2 \times ULN$
- Patients not biochemically euthyroid
- Patients who have any current or prior medical condition that can interfere with the conduct of the study or the evaluation of its results, such as
  - History of immunocompromise, including a positive HIV test result (Elisa and Western blot). An HIV test will not be required, however, previous medical history will be reviewed
  - Presence of active or suspected acute or chronic uncontrolled infection

- History of, or current alcohol misuse/abuse in the 12 month period prior to screening
- Female patients who are pregnant or lactating, or are of childbearing potential and not practicing a medically acceptable method of birth control. If a woman is participating in the trial then one form of contraception is sufficient (pill or diaphragm) and the partner should use a condom. If oral contraception is used in addition to condoms, the patient must have been practicing this method for at least two months prior to screening and must agree to continue the oral contraceptive throughout the course of the study and for 3 months after the study has ended. Male patients who are sexually active are required to use condoms during the study and for three month afterwards as a precautionary measure (available data do not suggest any increased reproductive risk with the study drugs)
- Patients who have participated in any clinical investigation with an investigational drug within 1 month prior to screening or patients who have previously been treated with seliciclib
- Patients with any ongoing or likely to require additional concomitant medical treatment to seliciclib for the tumor
- Patients with concomitant treatment of strong CYP3A4 inducers or inhibitors.

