## Section 6.0 Treatment of Subjects

Transsphenoidal pituitary tumor resection is the primary therapy for Cushing disease, and yields 30-70% surgical cure rates. Patients with recurrent or residual tumors, and/or are not surgical candidates typically undergo pituitary-directed radiation, adrenalectomy, treated with pasireotide, and/or medical suppression of adrenal gland cortisol production. In this study, we will treat patients with *de novo*, persistent, or recurrent Cushing disease with seliciclib during the period of evaluation and preparation for standard care, which usually takes 4 weeks at our center. We are excluding any subjects who need immediate surgical intervention, i.e. unstable visual field deficit, tumor compression of optic chiasm, or severe metabolic complications. We only will recruit those whom we would recommend for routine evaluation process for standard care. After completion of their participation in the study, subjects will be ready to start standard care. If a given patient responds to the study drug and chooses to stay on the drug after cessation of the trial, clinical data will continue to be collected for further analysis of drug response and monitoring safety.

Study calendar: baseline physical exam, vital signs, weight and laboratory evaluations will be conducted within 7 days prior to the start of therapy. Pituitary imaging and ECG will be performed within 60 days prior to the start of therapy. All procedures and evaluations may be performed within 3 calendar days of that specified in the protocol to accommodate patient convenience and scheduling. Patient informed consent will be obtained prior to any protocol-specific procedures. The schedule of study events is provided in Table 1.

Patients will be administered a dose of oral seliciclib 400 mg twice daily for 4 days every week for total of 4 weeks. Patients will be seen on days 1, 8, 15, 22 and 29 for repeat laboratory testing, assessment of treatment compliance, and toxicity according to National Cancer Institute Common Toxicity Criteria version 3.

The following tests will be performed:

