- Plasma ACTH and serum cortisol levels (every three hours from 9:00 – 15:00)
  - Blood draw will be done via intravenous catheter every 3 hours from 9AM to 3PM.
    - In the case that an intravenous catheter cannot be placed, one blood draw will be performed at every 3 hour interval.

- ECG
- 24 hour urinary free cortisol any time between days 24-28
  - Subjects will collect 3 - 24 hour UFC any time between days 24-28 prior to coming in for study visit 6
- 2 - late night salivary cortisol at 23:00-24:00 between days 24-28

Visit 6: Day #29

- History and physical exam
- Adverse events assessment
- CBC with differential, CMP (including fasting blood glucose), , PT/INR
- Fasting lipid profile, HbA1C
- Hormone profile: PRL, TSH, adjusted T4, free T4, IGF-1, LH, FSH, estradiol for females, testosterone (total and free) for males
- Serum Pregnancy Test (for females of childbearing potential)
- Plasma ACTH and serum cortisol levels (every three hours from 9:00 – 15:00)
  - Blood draw will be done via intravenous catheter every 3 hours from 9AM to 3PM.
    - In the case that an intravenous catheter cannot be placed, one blood draw will be performed at every 3 hour interval.
- ECG
- Visual Fields
- Pituitary MRI
- 24 hour urinary free cortisol on days any time between 30-35
  - Subjects will collect 3 - 24 hour UFC any time between days 30-35 prior to coming in for study completion visit
- 2 - late night salivary cortisol at 23:00-24:00 between days 30-35

Study Completion Visit: Day 36

- History and physical exam
- Adverse events assessment

Table 1. Study procedure flow sheet

Procedures	Screening Visit -60 to -1	Visit 1 Baseline	Visit 2 Day 1	Visit 3 Day 8	Visit 4 Day 15	Visit 5 Day 22	Visit 6 Day 29	Study Completion Visit
Standard of Care Procedures: Items, drugs and services that are part of regular care and would be done even if you did not take part in this research study. These will be billed to you and/or your insurance company.								
Visual Field Exam	X 							
MRI of the Pituitary	X 							
Research Related Procedures: Items, drugs and services done for research purposes only. These will be covered by the sponsor of the study and will NOT be billed to your insurance company.								
Review of medical records	X							
History and Physical Exam	X	X	X	X	X	X	X	X
Serum Pregnancy Test (for female of childbearing potential)	X	X	X	X	X	X	X	X

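### Pregnancy notification stops five days after treatment while the stated contraception period runs to 3 months after the study, and partner pregnancies have no notification rule

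*Combined protocol and SAP*

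**What the plan says.** Section 8.0 (Pregnancy) opens with "Patients who become pregnant during the study should discontinue the study immediately". It then tells patients to notify the investigator if it emerges after completion that "they become pregnant either during the treatment phase of the study or within five days after the treatment period". Where possible, a pregnancy is to be followed to its outcome for mother and child. The text speaks only of patients who become pregnant.

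The contraception rules are in the exclusion criteria of Section 5.0. A woman who uses oral contraception together with condoms "must agree to continue the oral contraceptive throughout the course of the study and for 3 months after the study has ended". For men the text reads "Male patients who are sexually active are required to use condoms during the study and for three month afterwards". It calls this precautionary and adds that "available data do not suggest any increased reproductive risk with the study drugs". No post-study duration is given for women using other methods.

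Three other places bear on the point:

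- **Additional SAE definitions (Section 8.0):** pregnancies are to be reported promptly to the institution's research compliance office. No post-study time limit is given.
- **Table 1:** a serum pregnancy test is marked at every visit, including completion. The narrative for the day 36 visit lists only history, physical examination and adverse events.
- **Regulatory and Reporting Requirements (Section 8.0):** adverse events are recorded until five days after the last dose.

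**The concern.** The protocol treats the 3 months after the study as a period in which pregnancy should be avoided, yet its notification instruction lapses within about a week of treatment ending. A patient who conceives in, say, the second month afterwards is inside the precautionary period but has not been asked to tell anyone. The follow-up of mother and child that Section 8.0 wants would then not start, because the investigator would not know.

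The position for men is starker. They carry a condom requirement during the study and for three months afterwards, but no instruction asks them to report a partner's pregnancy at any time.

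What is at stake is safety-data capture for a drug whose effect on pregnancy the protocol treats with caution. No efficacy conclusion depends on it.

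**Working it through.** The plan states no figure to reproduce. The check compares two time windows, counted in days from day 1.

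**Inputs**

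- Treatment is "oral seliciclib 400 mg twice daily for 4 days every week for total of 4 weeks" (Section 6.0). The treatment period therefore ends at T = day 28. If the clock starts at the last planned dose, with week 4 dosed on days 22 to 25, T = 25.
- Study end: "Study Completion Visit: Day 36", so E = 36. E = 29 (Visit 6) is used as a sensitivity value.
- Post-treatment notification allowance: 5 days (Section 8.0, Pregnancy).
- Post-study contraception: 3 months (Section 5.0), taken as M = 91 days. The range 84 to 92 is an assumption about what a month means.

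**Formulas**

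- Notification window N = T + 5
- Required contraception period C = E + M
- Share covered = N / C

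**Results for female oral-contraceptive users**

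| Case | N | C | Covered | Not covered |
|---|---|---|---|---|
| Base: T = 28, E = 36, M = 91 | 33 | 127 | 26.0% | 94 days, 74.0% |
| Lowest cover: T = 25, E = 36, M = 92 | 30 | 128 | 23.4% | 76.6% |
| Highest cover: T = 28, E = 29, M = 84 | 33 | 113 | 29.2% | 70.8% |

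**Crediting study testing.** Suppose every conception up to day 36 is counted as found by the serum tests. This is generous, since a very recent conception can be missed. The base case becomes 36/127 = 28.3% covered and 71.7% not covered. The range not covered is 68.1% (36/113 covered) to 71.9% (36/128 covered).

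**Post-treatment part alone.** In the base case the five days are 5/(127 − 28) = 5/99 = 5.1%. Across the assumptions the share is 4.9% to 5.9%.

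**Male patients.** The notification rule covers none of the period, because it does not mention partners.

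**The case against.** A fair defence has four parts.

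**The two windows serve different purposes.** The five days match the length of the adverse-event and SAE windows in Section 8.0, so the rule is consistent as a reporting convention. Nothing in the protocol says that a precautionary contraception period and a notification window must be equal. This stands as far as it goes: the documents support reconciling or explaining the difference, and do not show that five days is wrong in itself.

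**Other routes exist.** Table 1 tests for pregnancy through the completion visit, and pregnancies are to be reported promptly without a stated cut-off. Section 8.0 also counts congenital abnormality as serious, and it requires later SAEs thought possibly related to the drug to be reported whenever the investigator hears of them. It would therefore be too strong to say that all safety information is lost. But these reporting routes work only once the investigator knows, and testing ends with the study. The patient instruction is what would bring a later pregnancy to light, and it asks only about the short window.

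**Exposure is not established.** A reader might infer that most drug-exposed pregnancies would go unrecorded. The documents do not support that. Conceptions in female patients during dosing, the most clearly exposed, are inside the window. No half-life, washout or reproductive-toxicity figure is given, and the men's requirement is described as precautionary.

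**A smaller coverage figure is tempting.** A reader might divide 5 by about 90 and say that 6% of the contraception period is covered. That mixes two clocks: the five days run from the end of treatment and the 3 months from the end of the study. It also leaves out the treatment phase, which is covered. The share of the whole required period is about 26%.

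**Conclusion.** The mismatch is real and unreconciled. For women using oral contraception, the notification window covers about 33 of 127 days of the required contraception period, or about 26% (23% to 29% across the calendar assumptions). Partner pregnancies are not covered at all, and that gap does not depend on any assumption about drug clearance or window length.

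The limits are these:

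- The percentages are shares of calendar time. Reading them as shares of pregnancies would assume a constant chance of conception over the period.
- The explicit 3 months applies to oral-contraceptive users and sexually active men, not to every woman in the trial.
- The day counts assume dosing stops at week 4. Sections 4.0 and 6.0 allow responders to stay on the drug, and the pregnancy rule does not say how its window would apply to them.
- Whether conceptions after the five days are drug-exposed cannot be judged from the documents.

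This is a minor point about safety capture. With 16 patients few pregnancies are to be expected, and the primary analysis and the decision rule are untouched.

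**What to change.** Reconcile the Pregnancy text in Section 8.0 with the contraception text in Section 5.0. Extend the notification and follow-up instruction to the end of whatever contraception period the protocol states, or keep the shorter window and give the reason. Add an instruction that male patients notify pregnancies in partners over the corresponding period, with outcome follow-up where the partner agrees. This point takes no view on how long contraception itself should last.

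The cost is about one sentence in Section 8.0 and one in the patient instructions, plus a clause for partners. The downside is a small amount of extra contact after the study, on the base-case calendar up to about day 127, for at most 16 patients. No visit, dose or analysis changes.
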